9 STATISTICAL CONSIDERATIONS

All statistical analyses will be based on a pre-specified statistical analysis plan (SAP). This plan will be informed by preliminary data analysis done mid-way during the study to identify the presence of potential sources of bias, including but not limited to the distribution and nature of the data, confounding effects, and amount and type of missing data. Each metric of interest will be initially assessed descriptively. For categorical data, we will use rates as the outcome measures, excluding the missing and unknown cases. For continuous data, parametric (one-sample t-test), non-parametric (Wilcoxon signed rank test) or resampling approaches (bootstrap or jackknife techniques) will be used, as appropriate. Comparisons between metrics from recent, current-technology trials and the TRC-PAD metrics will be made using 95% confidence intervals. A p-value of 0.05 will be used to conclude significant differences between the two study groups. For comparisons of metrics across different sub-groups of interest, t-tests, chi-square tests or resampling techniques will be used, as appropriate for the type (continuous, categorical) and distribution (normal, non-normal) of the data. Regression models (generalized linear models or generalized linear mixed models), as appropriate, will be used to examine associations of covariates of interest with the TRC-PAD metrics.

All statistical analyses will be conducted at the end of the grant cycle with all available data at the point of data cut-off date. Due to the exploratory nature of these aims, no adjustments will be made for multiple comparisons. However, data will be reported as point estimates and confidence intervals to provide the magnitude and variability around each of the estimates. All analyses will utilize R (www.r-project.org).

Statistical Aim 1: This approach will markedly accelerate recruitment timelines, shorten time to site activation for trials, and reduce unexplained variance in cognitive testing.

Analysis Plan: The use of adaptive approaches to participant selection, data capture and data monitoring will continually optimize the approach. At the end of the five years, formal tests of hypotheses will be conducted to assess the success of the web-based mechanisms by quantitative and qualitative analysis, in particular comparing timelines, cost, screen failure rates and the measured change and variance in cognitive scores to those in preclinical and prodromal studies for which similar data can be obtained. Two-sided, one-sample tests of means (recruitment timelines and time to site activation) or variances (variance in cognitive testing) or corresponding resampling techniques will be used to detect differences between the TRC-PAD sample and comparator data.

Power Analysis: Power analyses for these hypotheses were done using a two-sided, one-sample t-test for means and a one-sample test of variance using the software PASS. A reduction of 10% in mean recruitment timeline, mean time to site activation and unexplained variance in cognitive testing is considered scientifically meaningful. While the sample size selected was based on the need for a Cohort sufficiently large to support an efficacy trial, we have examined the power of this sample to test our hypotheses. 1. A sample size of 2000 participants achieves 90% power to detect a change as little as 3 days (3%) in recruitment timelines and time to site activation for trials,

assuming current estimates of 120+/-40 days respectively. 2 Estimates of baseline variability from completed AD trials range between 4.5 and 10 points in ADASCog11 score within a site. A sample size of 2000 participants achieves 90% power to detect a difference of at least 0.4 points (5% change) in unexplained standard deviation of cognitive scores, assuming a type I error rate of 5%. Thus, there is adequate power to detect very small differences and looking at multiple sub-groups of interest would not compromise power.

Statistical Aim 2: Once optimized, this algorithm will be able to select amyloid positive individuals (and eventually tau and other neurodegenerative biomarkers) with >75% accuracy, greatly reducing future costly biomarker screen fails.

Analysis Plan: Initial amyloid PET results will be compared to historical data from preclinical and prodromal studies for which similar data can be obtained and, for prodromal participants, published data from gantenerumab and avagacestat studies. Standard statistical methods (t-tests for continuous measures and chi-square tests for categorical measures) will be used to compare the participants identified as biomarker positive and biomarker negative. Associations between an indicator of biomarker positivity and each of the potential risk factors will be assessed in a two-staged manner using a generalized linear model with a logit-link function or a generalized linear mixed model for binary data (to account for the measurements over time for an individual participant). Univariate associations deemed to be statistically significant ($p < 0.15$) will be included in a multivariable logistic regression model. Potential confounding and effect-modifying variables will be included in the model as covariates, if necessary. The risk factors and the appropriate functional form of these factors that will be utilized in the model will be clearly stated in the SAP and will be based on the results of the preliminary analysis. An individual participant's predicted risk of biomarker positivity will be calculated using the final multivariable risk prediction model and serve as a risk-algorithm. The performance of this model will be assessed using four measures: the concordance index (c-index) to evaluate the discrimination ability, the calibration slope and calibration in the large to evaluate the model calibration, and decision-curve analysis to assess clinical usefulness. The model will be internally validated using 10-fold cross-validation and bootstrap sampling.

Power Analysis: Power analysis was done using a comparison of the area under a ROC curve (AUC) with a null hypothesis value of 0.75. Assuming a total sample size of 2000 participants and a 60% amyloid expected positivity rate, we have 90% power to detect an AUC of at least 0.80 using a two-sided z-test and a level of significance of 5%.

Statistical Aim 3: Baseline and longitudinal cognitive performance, (including lack of practice effect on repeated web-based cognitive tests), decline on performance based functional measures, and a combination of self- and study-partner report will predict and subsequently track with in-person measures of cognitive (PACC) and functional (CDR-SB) decline.

Analysis Plan: To assess the associations between web-based cognitive tests and in-person measures, linear mixed models will be used to accommodate the dependencies of scores over the follow-up time period. Such models accommodate different times of measurement, time varying and time invariant covariates as well as missed measurements and data from participants who are lost to follow-up. Permutation tests may be implemented to verify that valid p-values will be obtained even if model assumptions are not correct.

Power Analysis: Assuming a correlation coefficient of 0.6 as the true correlation between these measures, we have 90% power to observe a correlation as low as 0.67 with a sample size of 1000 participants and a type I error rate of 5%. Hence, the sample size will have adequate power to detect clinically meaningful associations between the web-based and in-person measures of decline.

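### Aim 2 predictors and their forms are chosen at a mid-study look and then evaluated on data that include the same participants; the internal validation as described does not remove the resulting optimism

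*Combined protocol and SAP*

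**What the plan says.** Section 9 (Statistical Considerations) promises a pre-specified SAP, then says: "This plan will be informed by preliminary data analysis done mid-way during the study". The stated purpose of that look is "to identify the presence of potential sources of bias, including but not limited to the distribution and nature of the data, confounding effects", together with missing data. The list is open-ended.

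The Analysis Plan for Statistical Aim 2 gives the look a larger role. The risk factors and their functional form "will be clearly stated in the SAP and will be based on the results of the preliminary analysis".

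On the final data set, Section 9 says: "All statistical analyses will be conducted at the end of the grant cycle with all available data at the point of data cut-off date".

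Within Aim 2 there is a further data-driven step. "Univariate associations deemed to be statistically significant" at p < 0.15 go forward to the multivariable logistic model. On validation the plan says: "The model will be internally validated using 10-fold cross-validation and bootstrap sampling". The Aim 2 power analysis uses "a null hypothesis value of 0.75".

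The plan does not say whether the mid-way look is blinded to amyloid status, which modelling steps are repeated inside the resamples, or whether any participants are kept apart. No external validation of the final model is described.

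**The concern.** Checks of distributions and missing data do no harm to a later performance estimate. Choosing predictors and transformations because they relate to the outcome does. Noise variables, and forms that fit by chance in the first participants, are carried into the model, and the same participants then help to show that the model works. Cross-validation that starts from the chosen list re-estimates only the coefficients. Each left-out fold has already influenced which terms are in the model.

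The c-index, its confidence interval, the calibration measures and the decision curve would all inherit this. Aim 2 is meant to show that the algorithm can cut biomarker screen failures, so an optimistic AUC bears directly on its use in later trials.

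**Working it through.** **Inputs from Section 9, Aim 2.** N = 2,000; 60% positive, so 1,200 positive and 800 negative; null AUC 0.75; alternative 0.80; two-sided 5%; stated power 90%. I take these at face value.

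**Assumptions, because the documents are silent.** The look covers the first 1,000 participants and uses amyloid results; its selection rule is p < 0.15; the number of candidates varies from 20 to 200.

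**Step 1: the plan's own figure.** Hanley-McNeil variance: [A(1−A) + (n₁−1)(Q₁−A²) + (n₀−1)(Q₂−A²)]/(n₁n₀), with Q₁ = A/(2−A) and Q₂ = 2A²/(1+A).

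- At A = 0.75: (0.1875 + 1199×0.0375 + 799×0.08036)/960,000 = 0.0001139, so SE = 0.0107.
- At A = 0.80: (0.16 + 1199×0.02667 + 799×0.07111)/960,000 = 0.0000927, so SE = 0.0096.
- Power = Φ[(0.05 − 1.96×0.0107)/0.0096] = Φ(3.02) = 99.9%.

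The Obuchowski binormal variance gives SE 0.0116 and 0.0109, and power 99.4%. The stated 90% is therefore conservative. That is a separate discrepancy and does not affect this point.

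**Step 2: what a given optimism does to the comparison with 0.75.** If the true AUC is 0.75 and the estimate is optimistic by d, the chance of wrongly concluding that it is higher is 1 − Φ(1.96 − d/SE). For d = 0.01 this is 1 − Φ(1.96 − 0.94) = 15.3% with SE 0.0107, and 1 − Φ(1.96 − 0.86) = 13.5% with SE 0.0116.

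| Optimism d | Chance of wrongly concluding AUC > 0.75 |
|---|---|
| 0 | 2.5% |
| 0.005 | 6.3-6.8% |
| 0.01 | 13.5-15.3% |
| 0.02 | 40-47% |

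**Step 3: how much optimism is left after cross-validation.** In a simulation of 2,000 participants, five real predictors had log-odds 0.44 per SD and the rest were noise. Terms were chosen on the first 1,000. The full-sample 10-fold cross-validated AUC was compared with the model's AUC in 20,000 new subjects (40 runs per row, Monte Carlo SE about 0.002). In the data-chosen column, each predictor's form was picked as linear, square or cut-point.

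| Candidates | Linear terms only | Form also data-chosen |
|---|---|---|
| 20 | −0.002 | 0.005 |
| 50 | 0.000 | 0.010 |
| 100 | 0.009 | 0.023 |
| 200 | 0.016 | 0.042 |

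A separate simulation of the same question gave 0.003-0.009 (linear) and 0.007-0.030 (form chosen) for 20 to 100 candidates. When selection was repeated on each fold's training data, the optimism was −0.005 to 0.000. In a hold-out of the later 1,000 it was −0.006 to 0.003.

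Two limits apply. The true AUC in the simulation was about 0.70-0.73, so applying these values at 0.75 is an approximation. The table also leaves out the plan's later p < 0.15 screen on all data, which adds optimism of its own if it too sits outside the resampling.

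**Step 4: what a temporal validation can deliver.** With 1,000 later participants (600/400), the Hanley-McNeil SEs are 0.0151 and 0.0136. Power for 0.80 against 0.75 is Φ[(0.05 − 1.96×0.0151)/0.0136] = Φ(1.50) = 93.3%; Obuchowski gives 87.5%. With 500 later participants (300/200), power is 66.3% and 57.9%.

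**The case against.** The strongest reply is that outcome-driven selection at the look is inferred. Section 9 describes the look as a search for sources of bias, and places outcome screening in the final two-stage analysis. This stands in part: use of amyloid results is the likely reading, not a stated one. But it is hard to base risk factors for positivity, and their functional form, on a preliminary analysis that ignores positivity.

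A reader might infer more than the documents support in four ways.

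- *Internal validation can never remove this optimism.* It can, if every selection step is repeated in each resample (Step 3). The plan is silent on which steps are resampled.
- *The tests reuse the data that generated the hypotheses.* The 75% target is fixed in Section 3 and the 0.75 null in the Aim 2 power analysis. Only the model's content is data-informed. The 0.75 null also appears only in the power analysis; the Aim 2 Analysis Plan lists performance measures and no test.
- *The bias equals the apparent optimism of a screened model.* The planned estimate is cross-validated, and participants enrolled after the look did not shape the model. What remains is smaller, and near zero with few linear candidates.
- *The primary test must therefore be confined to later participants.* That would cut power from 99.4-99.9% to 87-93%, or to 58-66% with 500. Section 2.2 also refers those at highest risk under an algorithm that is iteratively updated. As an illustration, take a binormal score with true AUC 0.80 and refer the top 50-70% (assumed) on that score or a noisy version of it. The AUC among those referred falls to about 0.68-0.77. A sound model could fail such a test.

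Section 9 also calls the aims exploratory. That is its reason for not adjusting for multiplicity; it does not make an optimistic AUC or its confidence interval unbiased.

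**Conclusion.** The point holds in a limited form. Read together, the three statements in Section 9 set a rule under which the Aim 2 model is partly judged by the participants who shaped it, and the validation as described does not correct for this.

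The size depends on a candidate count and a freedom of form that the documents do not give. For 20 to 100 candidates it runs from negligible (linear terms, short list) to about 0.03 in AUC (forms chosen from the data). The upper end is more than half of the 0.05 gap between 0.75 and 0.80. Even 0.01, about one standard error, raises the one-sided error from 2.5% to 14-15%.

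This rests on the look using amyloid results, on its covering about half the sample, and on the stated 2,000 participants and 60% positivity. If the look is blinded to amyloid status, the concern falls away.

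**What to change.** In the SAP:

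1. State whether the mid-way look uses amyloid results, and list the candidate predictors and allowed forms.
2. Make the mid-way choice of predictors and forms a scripted rule. Repeat it, with the p < 0.15 screen, inside every cross-validation fold and bootstrap resample. Base the comparison with 0.75 and the calibration measures on that corrected estimate.
3. Freeze the model at the mid-way SAP lock. Report its AUC, calibration in the large and calibration slope in participants first amyloid-tested after that date, as a temporal validation alongside the main estimate.

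The cost is SAP wording, more computation and a slightly lower reported AUC, with no new visits or procedures. Choices made by judgement at the look cannot be repeated in a resample; for those, only item 3 gives a clean estimate. Its power is about 87-93% with 1,000 later participants and 58-66% with 500. It should be read knowing that later referrals are selected by the updated risk algorithm, which can lower the AUC for reasons unrelated to overfitting.

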2.3.1.4 PSYCHOLOGICAL RISKS OF REFERRAL FROM THE APT WEBSTUDY

When a participant is identified as having increased risk for future development of AD based on their profile and performance in the APT Webstudy, they will be contacted by email or phone to present for an in-clinic evaluation to have their increased risk explained and to consent for screening to join the in-clinic TRC-PAD cohort. Participants deemed ineligible at the in-clinic evaluation may be referred for further clinical evaluation of a non-AD diagnosis and/or returned to the APT Webstudy for continued tracking. Risks associated with this process include negative outlook based on the invitation for further evaluation of memory performance as part of the APT Webstudy. In the case of individuals referred from other studies where their amyloid status may be known, they might be referred to in-clinic evaluation to join the TRC-PAD cohort if eligible. These individuals may therefore bypass the APT Webstudy completely.

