8 STUDY ASSESSMENTS AND PROCEDURES

8.1 CLINICAL AND COGNITIVE ASSESSMENTS

8.1.1 PRESCREEN PHASE

During the prescreen phase, participants will be enrolled in the APT Webstudy and once triggered for increased risk of developing AD, will be referred to in-person clinical evaluation. Participants for whom evidence of brain amyloid has already been confirmed, may be referred for in-person clinical evaluation to participate in TRC and bypass the APT Webstudy.

Prior amyloid testing, when applicable, should be confirmed prior to screening.

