8.1.2.1 BIOMARKER CONFIRMATION USING SHARED IMAGES AND/OR RESULTS

Participants who have previously undergone amyloid testing via PET or CSF under another research study may provide consent to have their PET scan, CSF sample, PET scan results and/or CSF results shared with the Coordinating Center for the purposes of biomarker confirmation at Screening Stage 2.

In such instances, approval from the sponsor of the other research study may be required prior to sharing of data or images. The Coordinating Center will work with the site and, if needed, the study sponsor on securely transferring the relevant data, ensuring that no identifiable information is shared with the Coordinating Center. The following are examples of how data may be shared with TRC:

- PET scan or CSF sample – scan/sample will be submitted to the Coordinating Center using standard submission procedures for central analysis
- PET or CSF analysis results (e.g. quantitative data) – data will be transmitted from the study sponsor or site to the Coordinating Center for review and evaluation against TRC entry requirements
- A report indicating that the participant was deemed eligible for a particular study based on amyloid testing results – report will be transmitted from the study sponsor or site to the Coordinating Center for review and evaluation against TRC entry requirements

To the extent possible, data will be incorporated into the TRC data sets and will be shared along with other TRC data as described in Section 10, however this may not be possible if the study sponsor requires restrictions on data sharing with the site or with other investigators.

In the event that a participant consents to having prior results shared, but the study sponsor does not provide their approval for sharing, the site investigator will consult with the Coordinating Center to obtain approval prior to enrollment.

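### Aim 1 judges the web-based mechanisms without separating out direct referrals, who may bypass the Webstudy and have largely met the amyloid criterion already

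*Combined protocol and SAP*

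**What the plan says.** **What is tested.** In Section 9, the Statistical Aim 1 Analysis Plan states that "formal tests of hypotheses will be conducted to assess the success of the web-based mechanisms by quantitative and qualitative analysis". The comparators are outside preclinical and prodromal studies, and the plan lists the metrics to be set against them: "in particular comparing timelines, cost, screen failure rates and the measured change and variance in cognitive scores". One-sample tests of means (recruitment timelines, time to site activation) and of variances (cognitive testing) "will be used to detect differences between the TRC-PAD sample and comparator data". No test or analysis set is named for cost or screen failure.

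**Power.** "Power analyses for these hypotheses were done using a two-sided, one-sample t-test for means and a one-sample test of variance", and "A sample size of 2000 participants achieves 90% power to detect a change as little as 3 days (3%) in recruitment timelines", from a current estimate of 120 +/- 40 days. A 10% reduction is called scientifically meaningful.

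**Who is in the cohort.** The Synopsis and Sections 2.2, 2.3.1.4 and 8.1.1 allow direct referral of people whose amyloid status is known. Section 2.3.1.4 says: "These individuals may therefore bypass the APT Webstudy completely". Section 2.2 only encourages them to join the Webstudy. Footnote 3 of the Schedule of Activities lets Stage 2 be skipped with Coordinating Center approval. Section 8.1.2.3 permits a telephone eligibility discussion for those already told an earlier amyloid result.

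**When prior amyloid is confirmed.** Section 8.1.1: "Prior amyloid testing, when applicable, should be confirmed prior to screening". Section 8.1.2.1, however, says that such participants "may provide consent to have their PET scan, CSF sample, PET scan results and/or CSF results shared with the Coordinating Center" for confirmation at Stage 2. The Schedule of Activities puts informed consent at Stage 1.

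**The concern.** The result is attributed to the web-based mechanisms, but some cohort members may not have been selected by them. Elevated or intermediate amyloid is an entry requirement (Section 5.1, criterion 11). A person referred because of a known amyloid result has largely met it before screening begins, and may be spared the Stage 2 procedure as well. Adding such people tends to lower the failure rate and, probably, screening time and cost, even if the Webstudy algorithm selects no better than current recruitment. The comparison with outside studies would then mix a web effect with a route-mix effect, and Section 9 contains nothing that pulls them apart.

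**Working it through.** **Inputs from the documents.** N = 2,000; mean 120 days; SD 40 (the +/- read as an SD); two-sided alpha 0.05; meaningful reduction 10%, i.e. 12 days (Section 9). Current screen failure about 80% (Section 4.2). Expected amyloid positivity 60% (Section 9, Aim 2), so 40% negative.

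**Inputs assumed, because the documents do not give them.** Direct share q: 5% to 50%. Days saved per direct referral t: 14 to 60. Failure among direct referrals on any criterion: 10%. The 80% is a general rate, not stated to be amyloid-only, so it serves only as an illustration.

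**1. Reproduce the plan's power.** Standard error = 40/√2000 = 0.894 days. 3/0.894 = 3.35; 3.35 − 1.96 = 1.39; power = 91.8%, which agrees with the stated 90%. The detectable difference at 90% power is (1.960 + 1.282) × 0.894 = 2.90 days.

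**2. Shift in mean time with no web effect.** Shift = q × t, with q the direct share of those analysed.

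| Days saved t | Share giving 3 days (3/t) | Share giving 12 days (12/t) |
|---|---|---|
| 14 | 21% | 86% |
| 24 | 12.5% | 50% |
| 30 | 10% | 40% |
| 60 | 5% | 20% |

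**3. Chance of a significant result from mix alone.** Take q = 10% and t = 30, so the shift is 3 days. The mixture SD is √(40² + 0.1 × 0.9 × 30²) = 41.0. Then 3/(41.0/√2000) = 3.27, and 3.27 − 1.96 = 1.31, a probability of about 91%.

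**4. Pooled screen failure.** Pooled = (1 − q) × web rate + q × 10%, with q now the direct share of those screened.

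| q | Web rate 80% | Web rate 40% |
|---|---|---|
| 10% | 0.90 × 80 + 0.10 × 10 = 73.0% | 37.0% |
| 25% | 62.5% | 32.5% |
| 50% | 45.0% | 25.0% |

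The web route is unchanged down each column.

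**5. Power if only web-referred participants are tested.** Detectable difference = 3.242 × 40/√n. This gives 3.1 days at n = 1,800, 3.3 at 1,500 and 4.1 at 1,000 (direct shares of 10%, 25% and 50%). All are well below 12 days.

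**The case against.** **The aim is the whole system.** Section 3 states Aim 1 for an efficient, sustainable recruitment system, and direct referral is part of that program. This stands: the full cohort is a fair set for a claim about the system. It is not a fair set for the claim in the Analysis Plan, which is about the web-based mechanisms.

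**It may be handled later.** Section 9 calls the aims exploratory, defers detail to an SAP informed by a mid-study check for bias and confounding, and allows sub-group comparisons and covariate regression. That leaves room for an analysis by route. But entry route is not named, so the correction is possible rather than planned.

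**The TRC-PAD sample is named only for means and variances.** Correct. For cost and screen failure the point is that no set is defined, not that the whole cohort is prescribed.

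**Savings in time and cost are not certain.** Also fair. Section 8.1.2.1 describes approval by another sponsor and data transfer, which could use up some of the time saved. Lower failure is the firmer expectation; time and cost are probable.

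**Stronger readings that the documents do not support.** A reader might infer that direct referrals cannot fail on amyloid, or that a non-confirming prior result never enters the screening records. Skipping Stage 2 is optional and needs approval. Section 8.1.2.1 allows central analysis of the earlier scan or sample and review against entry requirements. Section 5.3 counts participants who miss any inclusion criterion as screen failures. A zero failure rate for this route is therefore too strong, particularly against a general 80% rate, since the other criteria in Sections 5.1 and 5.2 still apply.

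**Conclusion.** The point holds as a mismatch between what the Aim 1 tests are said to assess and the people they include. The direction for screen failure follows from the entry rules; for time and cost it is likely but not assured. The size cannot be fixed from the documents. On the assumed ranges, a direct share of 5% to 21% is enough to produce the 3-day shift that the test is powered for, but only a large share reaches the plan's own 12-day threshold on time alone. The screen failure figures depend on the assumed 10% and on the direct share.

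A reader might go further and conclude that a positive Aim 1 result would be spurious, or that time to site activation is distorted too. Neither follows: the mix is unknown, and site activation is not clearly affected by how individuals are referred.

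The order of confirmation is a separate, smaller matter. Section 8.1.1 could mean only that earlier testing is verified to have taken place, so this is an ambiguity more than a flat contradiction. It still bears on which non-confirming results are counted.

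**What to change.** 1. Record entry route for everyone who starts screening, defined by what triggered referral to TRC. Webstudy membership will not serve, because direct referrals are encouraged to join.
2. In the Aim 1 Analysis Plan, run the web-mechanism tests of recruitment timelines, cost and screen failure on all Webstudy-referred people who start screening, Stage 1 failures included. Report amyloid failure additionally among those reaching Stage 2. Limiting overall failure to people who undergo Stage 2 would be wrong: Section 8.1.2 requires central review of Stage 1 data first, so Stage 1 failures would drop out and the web route would be flattered.
3. Report direct referrals separately. Label any whole-cohort result as the recruitment system of Section 3, not the web mechanisms.
4. Reconcile Section 8.1.1 with Section 8.1.2.1 and the Schedule of Activities on when prior amyloid is confirmed relative to consent and screening, and count non-confirming prior results for the direct-referral route.

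**Cost.** One variable, some SAP wording and one protocol clarification. The web-mechanism tests rest on fewer participants, and the headline figures may be less favourable. Power is not an obstacle (step 5).

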1 PROTOCOL SUMMARY

1.1 SYNOPSIS

Title:	TRC-PAD Program: In-Clinic Trial-Ready Cohort (TRC)
Study Description:	Development of a large, well-characterized, biomarker-confirmed, trial-ready cohort to facilitate rapid enrollment into AD preclinical/prodromal trials utilizing feeder registries into the APT Webstudy and subsequent referral to in-clinic evaluation and biomarker confirmation. Participants with known biomarker status may have direct referral to the trial-ready cohort.
Objectives:	1. To build an efficient and sustainable recruitment system in order to enroll an initial TRC-PAD Cohort. 2. To optimize an innovative, adaptive risk algorithm to efficiently identify the most appropriate trial participants. 3. To develop and validate web-based cognitive and functional outcome measures for future clinical trials.
Study Population:	At least 2,000 (1,000 preclinical + 1,000 prodromal AD) trial-ready individuals aged 50-85
Description of Sites:	Approximately 60 AD clinical trials sites
Description of Study	No intervention
Intervention:	
Study Duration:	5 years
Participant Duration:	5 years

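### Aim 1 compares TRC-PAD with other studies' data using one-sample tests, so comparator sampling error is ignored: type I error exceeds 5% and power for the variance hypothesis is overstated

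*Combined protocol and SAP*

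**What the plan says.** All of this is in section 9, Statistical Considerations. The general text says "Comparisons between metrics from recent, current-technology trials and the TRC-PAD metrics will be made using 95% confidence intervals" and then "A p-value of 0.05 will be used to conclude significant differences between the two study groups". The Aim 1 Analysis Plan promises formal hypothesis tests at the end of five years. These compare timelines, cost, screen failure rates and the change and variance in cognitive scores "to those in preclinical and prodromal studies for which similar data can be obtained". The stated method is "Two-sided, one-sample tests of means (recruitment timelines and time to site activation) or variances (variance in cognitive testing) or corresponding resampling techniques".

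The Aim 1 Power Analysis follows the same approach: "Power analyses for these hypotheses were done using a two-sided, one-sample t-test for means and a one-sample test of variance". It sets the target: "A reduction of 10% in mean recruitment timeline, mean time to site activation and unexplained variance in cognitive testing is considered scientifically meaningful". With 2,000 participants it claims 90% power for a 3-day change, assuming 120 days with SD 40, and 90% power for a 0.4-point (5%) change in the SD of cognitive scores. It concludes: "Thus, there is adequate power to detect very small differences". Nowhere do the documents give the size or standard error of the comparator data, or say how its uncertainty will be carried into the test.

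**The concern.** The hypothesis concerns a difference between two estimated quantities, and the plan itself speaks of two groups. A one-sample test allows for sampling error in TRC-PAD only. If the comparator mean or variance comes from a finite study, the test rejects too often when nothing differs, and the power calculation leaves out the same source of variance. Section 9 does not say how the 95% confidence intervals will be built; if they are built the one-sample way, they are too narrow by the same factor.

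Two things are at stake. First, chance differences from past studies could be reported as significant gains in recruitment speed, site activation or measurement precision. Second, the claim of ample power may fail for cognitive variance. There the meaningful effect (10% in variance, about 5.1% in SD) is almost exactly the effect the plan is powered for, so nothing is held in reserve.

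**Working it through.** **Inputs from section 9:** n_TRC = 2,000; mean 120 days, SD 40; 5% change in SD (0.4 points, implying a reference SD of 8); two-sided alpha 5%; meaningful reduction 10%. **From the synopsis (section 1.1):** "Approximately 60 AD clinical trials sites". **Assumed, because the documents do not give it:** comparator size m, shown as a range; equal variances; normal scores; independent participants.

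**Step 1: reproduce the plan's figures with the comparator fixed.**
- Means: one-sample t-test, 3 days, SD 40, n = 2,000: power 91.8%. The change detectable with 90% power is 3.2415 × 40/sqrt(2000) = 2.90 days.
- Variance: one-sample chi-square test, SD 8 against 7.6: power 89.8%. For exactly a 10% variance reduction, 91.3%.

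Both agree with the stated 90%, so the calculation contains no comparator error.

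**Step 2: type I error when the comparator is itself a sample.** The true standard error of the difference is SD × sqrt(1/2000 + 1/m); the one-sample test uses SD × sqrt(1/2000). The ratio is sqrt(1 + 2000/m), so the true type I error is 2 × (1 − Φ(1.96/sqrt(1 + 2000/m))). At m = 2,000 the ratio is 1.414, and 1.96/1.414 = 1.386 gives 16.6%. For the variance test, the exact F distribution and simulation agree with this formula to within 0.3 percentage points over the sizes shown.

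**Step 3: power of a valid two-sample test for a variance ratio of 0.90** (exact F test with 1,999 and m − 1 degrees of freedom).

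| Comparator size m | Type I error of planned test | Two-sample power, 10% variance reduction |
|---|---|---|
| 500 | 38% | 33% |
| 1,000 | 26% | 49% |
| 2,000 | 17% | 65% |
| 5,000 | 10% | 80% |
| 10,000 | 7% | 86% |
| 20,000 | 6% | 89% |
| fixed constant | 5% | 91% |

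Power of 80% is reached at m of about 4,900.

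**Step 4: differences detectable with 90% power, for m = 500 / 1,000 / 2,000.**
- Days: 3.2415 × 40 × sqrt(1/2000 + 1/m) = 6.5 / 5.0 / 4.1, against 2.9 with a fixed comparator.
- SD: 3.2415 × sqrt(1/4000 + 1/(2m)) = 11.5 / 8.9 / 7.2%, against 5.1%. The exact F test for a reduction gives 10.8 / 8.5 / 7.0%.

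**Step 5: the meaningful effect on recruitment time.** Ten per cent of 120 is 12 days. The standard error of the difference is 2.00 / 1.55 / 1.26 days, so 12 days is 6 to 9.5 standard errors and power stays above 99%.

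**Step 6: site activation, if measured once per site.** Take 60 TRC sites, and assume SD 40 days across sites and 30 / 60 / 120 comparator sites. Type I error of the one-sample test is 26 / 17 / 11%. Two-sample power for 12 days is 26 / 37 / 47%, against 63% one-sample. The shortfall from 90% to 63% comes from counting sites instead of participants; only the further drop comes from comparator error.

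**The case against.** A one-sample test does hold its level if the null value is a benchmark fixed in advance. The power analysis uses 120 days, which could be read that way. But section 9 labels that figure a current estimate, and says the tests are to detect differences from comparator data. No fixed target is declared, and none is offered for cognitive variance, where the plan itself quotes comparator variability from 4.5 to 10 points.

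It can also be said that details are left to the SAP and that resampling is allowed. The resampling is described as corresponding to the one-sample tests, however, and resampling of both groups is not mentioned.

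The aims are called exploratory, and cohort size was not set by these calculations. Both statements are true. The exploratory label is used to waive multiplicity adjustment; the same section still promises formal tests at 0.05 and claims adequate power. No larger cohort is asked for here.

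Several points stand:
- The size of the error depends on an assumed comparator size; only its direction is certain.
- The stated 90% is correct for the test named; it is overstated for the question asked.
- The variance calculation uses ADASCog11, which is not among the assessments in the Schedule of Activities (section 1.3) or section 8.1.7, so the 0.4-point figure is not tied to a listed in-clinic score.
- Differences between non-randomised studies may exceed sampling error. If true comparator SDs varied by 5% between studies (assumed), a two-sample variance test at 2,000 against 2,000 would still reject about 42% of the time when TRC-PAD equals the average.
- The F test depends on normality: with excess kurtosis of 1 (assumed), its type I error is about 11%.

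The last two points limit what the correction can achieve. They do not justify omitting comparator error.

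**Conclusion.** The concern holds, and the plan is wrong as written. For any comparator drawn from a finite study, the planned tests exceed their 5% level: 38% at 500 comparator participants, 17% at 2,000, and still 6% at 20,000, assuming equal variances, normality and 2,000 TRC participants. The main practical consequence is for cognitive variance, where the claim of adequate power fails unless the comparator is large. For participant-level recruitment time the meaningful effect is safe, and the harm is limited to small chance differences being called significant. Site activation is exposed if it is analysed per site. Confidence is high in the direction; the amount cannot be fixed until the comparator sizes are stated. This should be fixed before the end-of-grant analysis.

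**What to change.** In section 9 and the SAP:

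- Replace the one-sample tests with two-sample comparisons that use the comparator's own n and SD. For times, use an unequal-variance t-test or the difference in means with a 95% CI. For cognitive variance, use the variance ratio with a CI.
- Use a two-sample bootstrap, resampling both groups, only where individual comparator data are available.
- Where a comparator's n or SD cannot be obtained, report the comparison descriptively without a p-value.
- Restate the detectable differences and the adequate-power sentence over a stated range of comparator sizes.

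A separate, secondary change is to use site-clustered standard errors for participant-level means. With 60 sites (about 33 participants each) and an assumed ICC of 0.01 to 0.05, the design effect is 1 + 32.3 × ICC = 1.32 to 2.62. Ignoring clustering then gives a type I error of 9 to 23% for means by itself, but only about 5 to 6% for the variance test.

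The cost is SAP wording and a recalculated power paragraph, with no change to TRC data collection. Comparator n and SD must be obtained, so some comparisons may become descriptive only. The restated figures will be less favourable (for SD, roughly 7 to 11.5% detectable instead of 5% for comparators of 2,000 down to 500). A two-sample test does not remove non-randomised differences between studies, and the report should say so.
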